## 16 HEALTH ECONOMICS OUTCOME AND WORK PRODUCTIVITY DATA

The health economics outcome and work productivity data will only be collected for subjects in US sites. The following questionnaires will be collected:

- Work Productivity and Activity Impairment Questionnaire: CRPS (WPAI: CRPS) assessment on Day 1, at Week 26, and at Week 52.
- Medical resources utilization and health economics data collection on Day 1, at Week 26, and at Week 52.

All data will be analyzed overall, i.e., for the single treatment group neridronic acid 400 mg, for the FAS. All data will be presented in subject data listings.

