## 8 ANALYSIS CONVENTIONS

### 8.1 General principles

If 2 or more of the population sets as defined in the SAP coincide, presentations will only be prepared for 1 population.

All presentations will be done overall, i.e., for the single treatment group neridronic acid 400 mg. The data collected and derived in the trial will be presented in subject data listings.

Data collected in this trial will be summarized according to their nature as follows:

- Continuous variables: number of non-missing observations, arithmetic mean, standard deviation, minimum and maximum values, median and quartiles. If there are less than 5 observations, descriptive statistics will be presented based on the rules specified in Section 20.1.1.2.
- Categorical variables: absolute and relative frequencies. If not defined otherwise, the percentage denominator will be the number of subjects still in the trial at the respective time point in the analyzed population.
- Time-to-event variables: number of subjects, number of subjects with event, number of censored subjects, first quartile, median, and third quartile including 95% confidence interval. For calculating the survival estimate confidence interval (CI) bounds, the log-log transformed estimate of CI bounds will be used. In addition, Kaplan-Meier estimates and plots will be provided with the respective number at risk and the Kaplan-Meier estimates at the relevant time points together with the median and its 95% CI. Censoring mechanisms will be described in the respective section.

Medical terms (e.g., prior and concomitant diseases, adverse events) will be coded via Medical Dictionary for Regulatory Activities (MedDRA), and medications will be coded according to World Health Organization Drug Dictionary (WHO-DD).

[Table 1](#) shows the use of analysis sets in different analyses as defined in Section 9.

Table 1: Use of analysis sets

	Enrolled Set	Allocated Set	SAF	FAS	TCS	PD Set
Subject disposition	X					
Discontinuations		X				
Protocol deviations			X			
Demographics			X			
Other baseline characteristics			X			
Subject medical history			X			
Previous and concomitant medication			X			
Exposure			X			
Compliance			X			
Primary safety endpoint			X			
Secondary safety endpoint			X			
Secondary efficacy endpoints				X	X	
Adverse events			X			
Laboratory values			X			
Vital signs			X			
Twelve-lead ECG			X			
Physical examination			X			
Bone turnover markers						X
Health economics data				X		

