Pooling of sites	
Individual sites will be combined to achieve pooled sites of similar size and with a sufficient number of subjects. Sites will be pooled by geographical region. The majority of sites are located in the United States of America (USA). Sites in the USA will be pooled in 4 regions based on United States (US) states:
 
 
• US North East: Connecticut (CT), Delaware (DE), Illinois (IL), Indiana (IN), Maine (ME), Maryland (MD), Massachusetts (MA), Michigan (MI), New Hampshire (NH), New Jersey (NJ), New York (NY), Ohio (OH), Pennsylvania (PA), Rhode Island (RI), Vermont (VT), and Washington D.C. (DC).
 
• US South East: Alabama (AL), Florida (FL), Georgia (GA), Kentucky (KY), North Carolina (NC), South Carolina (SC), Tennessee (TN), Virginia (VA), and West Virginia (WV).
 
• US Midwest: Arkansas (AR), Colorado (CO), Iowa (IA), Kansas (KS), Louisiana (LA), Minnesota (MN), Mississippi (MS), Missouri (MO), Montana (MT), Nebraska (NE), New Mexico (NM), North Dakota (ND), Oklahoma (OK), South Dakota (SD), Texas (TX), Wisconsin (WI), and Wyoming (WY).
 
• US West: Alaska (AK), Arizona (AZ), California (CA), Hawaii (HI), Idaho (ID), Nevada (NV), Oregon (OR), Utah (UT), and Washington (WA).
 
 
The sites in Europe will be pooled in one region, European Union (EU).

Pre-treatment-period	Before first IMP administration (excluded), i.e., the period between signature of the informed consent form and first administration of IMP.

Term	Definition
Subjects discontinued from treatment	Subjects permanently discontinued from IMP, i.e., subjects who stopped treatment prior to, or at any time during Visit 2, 3, 4, or 5.
Treated subjects	Subjects with at least 1 administration of IMP, including partial infusions.
Treatment period	The treatment period includes the four infusion visits starting at Visit 2 up to Visit 5. If a subject is permanently discontinued from treatment, the treatment period ends at the visit of the last infusion.
Treatment completers	Treated subjects who completed IMP administration according to the protocol, i.e., subjects who received the full dose of all 4 planned infusions of IMP. Treatment completers form the Treatment Completers Set defined below.
Trial completers	All subjects completing Visit 11 according to the protocol.

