### 9.4 Full Analysis Set

The Full Analysis Set includes all subjects allocated with at least 1 IMP administration, including any partial infusion. In this trial, the Full Analysis Set coincides with the Safety Set.

Analysis on the FAS will be conducted according to the allocated treatment. In this single-arm trial, the allocated treatment is the same as the actual treatment.

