### 16.2 Medical resources utilization and health economics data

The medical resources utilization and health economics questionnaire has 6 categories:

- Hospitalization.
- Emergency room visit.
- Nursing home stay.
- Outpatient care provider contact.
- Home services and help.
- Special product/device/tool.

For the categories hospitalization, emergency room visit, nursing home stay, and special product/device/tool, the use of these services will be descriptively summarized as a categorical variable (Yes/No/Don't know).

For the categories outpatient care provider contact, and home services and help, the use of each service type within the 2 categories will be descriptively summarized as a categorical variable (Yes/No/Don't know).

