**20.1.1.7 Handling of missing values**

At each time point/visit, all subjects still in the trial are reported. Missing values will be taken into account as missing in the analysis. The number of observed values and the number of missing values must sum up to the number of subjects in the trial at the respective time point/visit.

Missing measurements/missing values are identified by the SDTM variable \*\*STAT=ND. If this variable is not recorded (it's a permissible variable) the missing values of \*\*ORRES should be used.

Unless otherwise specified in the SAP, missing values will not be imputed.

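### Health-economics data are collected only at US sites but summarised on the whole Full Analysis Set, so EU subjects lower every service-use percentage and count as missing

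*SAP*

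**What the plan says.** SAP Section 16 opens with the restriction on collection: "The health economics outcome and work productivity data will only be collected for subjects in US sites". The protocol agrees in Section 1.2, the schedule of events, the visit lists and Section 12.6.

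The same SAP section then sets the population: "All data will be analyzed overall, i.e., for the single treatment group neridronic acid 400 mg, for the FAS". Table 1 of the SAP also places health economics data under the FAS. Section 9.4 defines that set with no regional limit: "The Full Analysis Set includes all subjects allocated with at least 1 IMP administration, including any partial infusion". European sites take part and form one pooled region under Section 8.2.2.

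For the resource-use questionnaire, Section 16.2 says of hospitalization, emergency room, nursing home and device use that "the use of these services will be descriptively summarized as a categorical variable", with levels Yes, No and Don't know. Outpatient contacts and home services are handled the same way by service type. Neither 16.1 nor 16.2 gives a denominator.

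Two general rules fill the gap. Unless something else is defined, Section 8.1 says that for categorical variables "the percentage denominator will be the number of subjects still in the trial at the respective time point in the analyzed population". Section 20.1.1.7 adds: "The number of observed values and the number of missing values must sum up to the number of subjects in the trial". Protocol Section 14.1.10 asks only for a descriptive summary and names no analysis set.

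**The concern.** EU subjects are never asked these questions, so they can contribute neither a Yes, a No nor a Don't know. Under the stated rules they still sit in the denominator of every service-use percentage and in the missing count at each of the three assessments.

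This has two consequences. The reported percentages understate service use among the subjects who were asked, always in the same direction. Absence by design also becomes indistinguishable from poor questionnaire completion, so the completeness of the US data cannot be read from the table.

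A third consequence is conditional. If dropout differs between the US and the EU, the US share changes from visit to visit, and a comparison of the Day 1 and Week 52 percentages would move for reasons unrelated to service use.

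**Working it through.** The plan states no figure to reproduce. The sample size of about 290 in SAP Section 5.2 comes without a rate or a power calculation and serves here only as a base for illustration.

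**Inputs**
- Data exist for US-site subjects only (SAP Section 16).
- Analysis set: FAS, all regions (SAP Sections 16 and 9.4, Table 1).
- Denominator: FAS subjects still in the trial at the visit (SAP Section 8.1).
- Observed plus missing equals all subjects in the trial (SAP Section 20.1.1.7).
- Planned N: about 290 (SAP Section 5.2).
- EU share of subjects: not given. SAP Section 8.2.2 says only that most sites are in the USA. A range is assumed.

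**Formula.** Let x be the number of US subjects answering Yes, and N_US and N_EU the numbers still in the trial.

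- Percentage among those asked: x / N_US
- Percentage as the SAP is written: x / (N_US + N_EU) = (x / N_US) × (1 − EU share)
- Missing by design: N_EU / (N_US + N_EU) = EU share. Any US non-completion comes on top.

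**For an assumed true rate of 20%**
- 10% EU: 0.20 × 0.90 = 18%
- 20% EU: 0.20 × 0.80 = 16%
- 30% EU: 0.20 × 0.70 = 14%

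**In whole subjects, N = 290, no dropout, true rate near 30%**

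| Assumed EU share | EU / US subjects | US users | Among US subjects | As written (÷ 290) | Missing by design |
|---|---|---|---|---|---|
| 5% | 14 / 276 | 83 | 30.1% | 28.6% | 4.8% |
| 10% | 29 / 261 | 78 | 29.9% | 26.9% | 10.0% |
| 20% | 58 / 232 | 70 | 30.2% | 24.1% | 20.0% |
| 30% | 87 / 203 | 61 | 30.0% | 21.0% | 30.0% |
| 40% | 116 / 174 | 52 | 29.9% | 17.9% | 40.0% |

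**Work productivity.** Section 16.1 treats the employment question as a 0/1 variable and takes its mean, which uses non-missing values only. At a 20% EU share with 93 employed US subjects, the result stays 93/232 = 40.1%; it does not fall to 93/290 = 32.1%. Only the missing count grows, by 58. The same holds for other work-productivity items summarised as continuous.

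**Change over time.** If the EU share of those still in the trial rose from 20% at one visit to 25% at a later one (both assumed), a constant true 20% would be reported as 0.20 × 0.80 = 16.0% and then 0.20 × 0.75 = 15.0%.

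**The case against.** The best defence is that Section 16 should be read as a whole. It begins by limiting collection to US sites, so the data to be analysed can only be US data, and the word overall may mean no more than that there is one treatment group. The Section 8.1 default yields wherever something else is defined, and a sensible programmer would apply the restriction. But the sentence on collection does not define a denominator, and the sentence on analysis names a set that includes EU subjects. Elsewhere the SAP says so when it wants another base: Sections 10.1 and 10.2 state theirs, and the other US-only data, from bone biopsy and imaging, have their own sets in Sections 9.7 and 9.8. Under Section 3 a contract research organization carries out the analysis according to the SAP, so getting the right percentage would mean departing from it.

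Second, Section 20.1.1.7 also says that missing values are recognised by a not-done flag or an empty result field, and a questionnaire never scheduled in the EU may produce neither. That describes how missing values are identified. It does not cancel the requirement that observed and missing values together account for every subject in the trial.

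Several limits do stand:
- The dilution is confined to the Section 16.2 percentages.
- The EU share is unknown and could be small, given that most sites are in the USA.
- The documents give no evidence of different dropout by region, and Section 16.2 plans no formal analysis of change.
- The error could be undone by a careful reader: absolute counts are reported, Section 10.1 gives FAS numbers by country, and all data are listed.
- Protocol Section 1.2 places these data outside the endpoints.

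**Conclusion.** The concern holds. The analysis set and the default denominator are both stated, and together they give the wrong percentage for every service-use item in Section 16.2. Each Yes, No and Don't know percentage is multiplied by one minus the EU share, and missing counts rise by at least that share at every assessment. With 290 subjects and an assumed 20% EU share, 70 US users would be reported as 24.1% where 30.2% is correct, and 58 subjects would be counted as missing although they were never asked.

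The size depends entirely on the EU share, which the documents do not give; the direction does not. The effect on comparisons between visits arises only if that share changes over time. Because the data are descriptive and outside the primary and secondary endpoints, this should be corrected but does not threaten the trial's conclusions.

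**What to change.** In SAP Section 16, replace the population with FAS subjects at US sites, and mark the health economics row of Table 1 the same way, for instance with a footnote. Add that percentages and missing counts for both questionnaires use US-site FAS subjects still in the trial at the visit, so that EU subjects are not counted as missing.

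With that base the dilution factor becomes 1: in the 20% illustration the table would show 70/232 = 30.2%, and the missing count would reflect only US non-completion. The cost is one sentence, a table note and a site filter in the programs. No data are lost and no other analysis changes.

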### 16.1 Work Productivity and Activity Impairment Questionnaire: CRPS

Answers to the 6 questions of the WAPI: CRPS questionnaire will be descriptively summarized by visit. The answers to question 1 (Are you currently employed: Yes/No?) will be assigned a dichotomous value (1 = Yes; 0 = No) and summarized as a continuous variable, i.e., the proportion of employed subjects will be derived.

### 16.2 Medical resources utilization and health economics data

The medical resources utilization and health economics questionnaire has 6 categories:

- Hospitalization.
- Emergency room visit.
- Nursing home stay.
- Outpatient care provider contact.
- Home services and help.
- Special product/device/tool.

For the categories hospitalization, emergency room visit, nursing home stay, and special product/device/tool, the use of these services will be descriptively summarized as a categorical variable (Yes/No/Don't know).

For the categories outpatient care provider contact, and home services and help, the use of each service type within the 2 categories will be descriptively summarized as a categorical variable (Yes/No/Don't know).

## **17 INTERIM ANALYSIS**

### **17.1 Interim analysis of efficacy**

Not applicable.

### **17.2 Interim analysis of safety**

An external, independent DMC will periodically review safety information from the trial and monitor trial conduct and overall progress.

The DMC will have the ability to make recommendations to the sponsor that might impact the future conduct of the trial. Procedures for and management of the DMC will follow the sponsor's standard operating procedures and will be documented in the DMC Charter. The DMC for this trial is anticipated to convene approximately every 6 months, depending on subject accrual in the trial.

The safety analyses provided to the DMC for each review meeting will be defined in a separate SAP.

## 19 CHANGES TO THE SAP

### 19.1 Changes from pre-final to final version

Not applicable.

### 19.2 Amendments

Changes were made from Final SAP (Version 1.0) to SAP Amendment 01 (Version 2.0). All the changes are documented in Section 7.3.

## 20 APPENDIX

### 20.1 Data derivation and analysis rules

The purpose of this section is to give technical details for the implementation of the SAP.

#### 20.1.1 General specifications

##### 20.1.1.1 Percentages and decimal places

If not otherwise specified, the following rules are applied:

- Percentages are presented to 1 decimal point.
- Percentages equal to 0 or 100 are presented as such without a decimal point.
- For descriptive summary statistics, the same number of decimal places as in the raw data are presented when reporting minimum and maximum values, 1 more decimal place when reporting mean, median, quartiles and confidence interval (CI) and standard deviation (SD).
- P-values are presented to 3 decimal points. P-values <0.001 will be reported as such.
- Ratios are presented to 3 decimal points.

The above described displaying rules must not be changed (e.g., rounding) for the integrated clinical trial report (ICTR) text and are used 1:1 in the body report as well. For analysis of pharmacokinetic data see also Section 20.1.5.

##### 20.1.1.2 Presentation of descriptive statistics

Calculation of mean: if not otherwise specified, the arithmetic mean is used.

Table 6: Presentation of descriptive statistics in clinical trials

Number of non-missing values	n	Missing n	Mean	SD	Min	Q1	Median	Q3	Max	{CI for mean}
0	+	+	-	-	-	-	-	-	-	-
1.2.3.4	+	+	+	-	+	-	+	-	+	-
≥5	+	+	+	+	+	+	+	+	+	+

+ summary statistic will be presented; - summary statistic will not be presented.

n = number of values; Min = minimum; Max = maximum; SD = standard deviation; Q1 = first quartile; Q3 = third quartile.

**20.1.1.3 Presentation of differences and changes**

For changes from baseline, the post-baseline value will constitute the minuend and the baseline value the subtrahend, i.e.,  $change = value - baseline$ .

**20.1.1.4 Trial day count**

The day of allocation/baseline visit / first IMP is defined as trial Day 1.

Calculate the trial day according to the following rules:

- If date < trial Day 1 then trial day = Date – trial Day 1
- If date ≥ trial Day 1 then trial day = Date – trial Day 1 + 1

**20.1.1.5 Presentation of units**

If applicable, parameters will be displayed together with the used unit of measurement. The unit of measurement is enclosed in square brackets ([ ]).

**20.1.1.6 Presentation of dates**

Where applicable (e.g., in listings), dates will be displayed in ISO8601 format (example: 2014-09-29T12:16, see CDISC 2013 V3.2). In case of incomplete dates, both the original value and the imputed value are displayed.

**20.1.1.7 Handling of missing values**

At each time point/visit, all subjects still in the trial are reported. Missing values will be taken into account as missing in the analysis. The number of observed values and the number of missing values must sum up to the number of subjects in the trial at the respective time point/visit.

Missing measurements/missing values are identified by the SDTM variable \*\*STAT=ND. If this variable is not recorded (it's a permissible variable) the missing values of \*\*ORRES should be used.

Unless otherwise specified in the SAP, missing values will not be imputed.

**20.1.1.8 Visit windows**

Not applicable.

**20.1.1.9 Assessments of on-treatment-period**

For the calculation of the on-treatment-period the date and time information given for IMP administration will be used according the definition in Section [8.2.2](#).

**20.1.1.10 Conversion of time intervals**

If a time interval was calculated in minutes, hours or days and needs to be converted into months or years the following conversion factors will be used:

- 1 month = 30 days
- 1 year = 365.25 days

**20.1.1.11 End of treatment**

End of treatment is the date of last administration of IMP given on the End-of-trial page in the eCRF.

**20.1.1.12 Mandatory tables without data**

Recommended tables must be created. If no subject qualifies for the table, the header will be created and the table itself will be replaced by “No subject in this category”.

**20.1.1.13 Kaplan-Meier analysis**

No additional specifications.

**20.1.1.14 Handling of data from early termination visits**

Subjects who discontinue during the trial the before their Visit 11 will be requested to undergo an early termination visit with identical procedures to Visit 11. Procedures done at Visit 11 are listed in the schedule of events of the protocol.

If the last available visit is between Visit 2 and Visit 7, data from the early termination visit will be assigned to the next scheduled visit; otherwise data will be assigned to the nearest scheduled visit based on the trial day of the early termination visit and the planned visit day. The planned visit day is:

- Day 182 for Visit 9 (Week 26).
- Day 273 for Visit 10 (Week 39).
- Day 365 for Visit 11 (Week 52).

In case of equal distance to 2 scheduled visits, the earlier visit will be chosen. If the assigned visit already occurred before the early termination visit, the data will be assigned to the next scheduled visit.

Data from the early termination visit will be analyzed using the re-assigned visits.

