#### 13.2.1.1 Current pain intensity

Current pain intensities and the corresponding changes from baseline will be presented in a subject data listing. Baseline current pain intensities will be flagged in the listing. Current pain intensities including their changes from baseline will be descriptively summarized by visit.

The change from baseline values at all post-baseline visits from Visit 3 through Visit 11 will be analyzed using a mixed model for repeated measures (MMRM), including the covariate baseline pain intensity, and the factors pooled site and visit as fixed effects, and subject as random effect. An unstructured covariance matrix will be used to model the covariance structure. The degrees of freedom of the denominator will be estimated using the Kenward-Roger approximation ([Kenward and Roger 1997](#)).

If the default Newton-Raphson algorithm used by statistical analysis software (SAS) PROC MIXED fails to converge, the Fisher scoring algorithm up to iteration 2 will be used (via the SCORING=2 option of the PROC MIXED statement) to obtain the initial values of covariance parameters ([Mallinckrodt et al. 2008](#)). If this alternative also fails to converge, then in addition the no-diagonal factor analytic structure (via the TYPE=FA0(T) option of the REPEATED statement, where T=9 is the total number of post-baseline visits, visits 3 to 11) will be used, which effectively performs the Cholesky decomposition of the covariance matrix and is numerically more stable. The first algorithm that leads to convergence in this sequence of fallback measures will be the algorithm used for the primary analysis of the trial.

Point estimates (LSmeans), standard errors, and 95% CIs for the factor visit in the MMRM model representing the change from baseline at each visit will be presented. A graphical plot of the model-based estimates and the 95% CI of the change from baseline of current pain intensity scores will be created.

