#### 13.2.1.2 Response to treatment

For each subject, the percentage change from baseline in current pain intensity will be calculated at each post-baseline visit (Visit 3 through Visit 11):

$$\%Change = \frac{Pain\ Intensity - Baseline}{Baseline} \cdot 100\%.$$

If the decrease is at least 30%, at least 50%, or at least 2 points on the NRS, the subject will be considered a responder for the respective threshold. If a subject shows a worsening or the pain intensity score is missing, the subject will not be considered a responder. This applies also to subjects with premature discontinuation where subsequent pain values are missing.

The percentage change from baseline, and the responder status (responder *Yes/No*) with respect to the 3 responder definitions will be presented in a subject data listing.

Descriptive summaries of the responder status will be presented by visit for each of the 3 responder definition. This includes the summary of the secondary responder endpoints, i.e., the response to treatment defined as at least 30%, at least 50% and at least 2 points on the NRS decrease from baseline at Week 12 (Visit 8) and Week 26 (Visit 9).

A graphical plot of the responder rates will be created by responder definition and visit.

For each of the 3 responder definitions, persistence of the treatment effect will be assessed by deriving a combined responder status for the following 3 time periods:

- Months 3 and 6 (Visit 8, and 9).
- Months 3, 6, and 9 (Visit 8, 9, and 10).
- Months 3, 6, 9, and 12 (Visit 8, 9, 10, and 11).

A subject is a combined responder if he/she is a responder at each of the visits mentioned in the definition of the respective time period. For the derivation of the combined responder status, the results of the individual visits are combined.

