#### **13.2.1.3 Patient Global Impression of Change**

The PGIC will be assessed at Visit 7 through Visit 11. Subjects respond to the question “Since the start of the trial, my overall status is:” with 1 of 7 possible responses (very much improved, much improved, minimally improved, no change, minimally worse, much worse, very much worse). A response of “very much improved” or “much improved” is generally regarded as a clinically important outcome. The response to treatment based on the PGIC will be derived by classifying subjects with outcome “very much improved” or “much improved” as responders, and subjects with other outcomes as non-responders. Subjects with missing PGIC score will be considered as non-responders.

All PGIC scores and the derived responder status will be presented in a subject data listing.

A descriptive summary of the categorical PGIC scores and the responder status will be generated by visit. This includes the summary of the secondary PGIC endpoints at Week 12 and Week 26.

A graphical plot of the distribution of the PGIC will be created by visit.

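### The early-termination rule has no distance limit, so a subject who left on Day 85 can count as a Week 26 responder and as a persistent responder for Months 3 and 6

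*SAP*

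**What the plan says.** SAP 20.1.1.14 has three parts.

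- If the last available visit was Visit 2 to Visit 7, the data go to the visit that follows. Later than that, they go to the closest one: "data from the early termination visit will be assigned to the next scheduled visit; otherwise data will be assigned to the nearest scheduled visit".
- If that visit has been used, the data move on: "If the assigned visit already occurred before the early termination visit, the data will be assigned to the next scheduled visit".
- The data are then analysed under the new visit label.

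No part limits the distance, and SAP 20.1.1.8, on visit windows, reads only Not applicable. The early-termination visit repeats the Visit 11 procedures (Protocol 9.3.3.1), so it yields pain scores and a PGIC rating (Protocol 11.1.3.6).

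The responder sections treat absence as failure. A missing pain score makes a subject a non-responder, and SAP 13.2.1.2 adds: "This applies also to subjects with premature discontinuation where subsequent pain values are missing". SAP 13.2.1.3 does the same for PGIC: "Subjects with missing PGIC score will be considered as non-responders". Persistence is a combined status requiring response at Visits 8 and 9, at Visits 8 to 10, or at Visits 8 to 11.

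For the MMRM, SAP 13.2.1.1 states: "The change from baseline values at all post-baseline visits from Visit 3 through Visit 11 will be analyzed". SAP 13.2.2 plans no sensitivity analysis.

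**The concern.** The rule fills a later visit with a score taken before that visit was due, from someone who has already left. The missing-value provision then never applies, and a subject whom SAP 13.2.1.2 would count as a failure can count as a success. The combined status suffers most: it is meant to show that response lasted, yet it can rest on two scores taken a day apart.

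Pain response and PGIC at Weeks 12 and 26 are secondary efficacy endpoints, and the combined status is the only analysis the SAP labels as assessing persistence. Because a missing value is a non-response, moving an early score into an empty visit can raise the responder count or leave it unchanged, never lower it. The effect on the rate depends on a denominator that SAP 13.2.1.2 does not state. No direction is claimed for the MMRM, but nothing planned would show how much the re-assignment contributes.

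**Working it through.** **Inputs**

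- Planned days: 182 (Visit 9), 273 (Visit 10) and 365 (Visit 11), from SAP 20.1.1.14. None is listed for Visits 7 and 8; weeks × 7 gives Days 42 and 84.
- Protocol windows (Protocol 1.6): ±7 days at Weeks 6 and 12; ±15 days at Weeks 26, 39 and 52.
- Sample size: about 290 (Protocol 1.5.1).
- Dropout, its timing, early-termination (ET) attendance and ET response are not in the documents. All are assumed below.

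**Planned days reproduced.** 26 × 7 = 182 and 39 × 7 = 273 agree with the SAP. 52 × 7 = 364 is one day below the stated 365, which is immaterial here.

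**Step 1: where a Day 85 score goes.** Visit 8 took place on Day 84.

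- If only the three listed visits are candidates, Day 182 is nearest, so the score goes to Visit 9.
- If all visits are candidates, Visit 8 is nearest but has occurred, so the score moves to Visit 9.

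Both readings agree, for any Visit 8 day from 77 to 84; the two scores are then 1 to 8 days apart. If the last visit was Visit 7, the Day 85 score goes to Visit 8 and no Week 26 responder arises.

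**Step 2: largest gaps**

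| Last visit (day) | ET day | Filed at | Days early |
|---|---|---|---|
| Visit 7 (42) | 43 | Week 12 | 84 − 43 = 41 |
| Visit 8 (84) | 85 | Week 26 | 182 − 85 = 97 |
| Visit 9 (182) | 183 | Week 39 | 273 − 183 = 90 |
| Visit 10 (273) | 274 | Week 52 | 365 − 274 = 91 |

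Under the strict count (first infusion is Day 1, Visit 7 is 42 days after Visit 2), Visits 7 and 8 fall on Days 43 and 85. The first two gaps become 85 − 44 = 41 and 182 − 86 = 96.

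With Visit 8 on Day 84 and no Visit 9, ET Days 85–227 (143 days) all map to Week 26. Of these, 31 (Days 167–197) are in window and 82 (Days 85–166) are too early.

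**Step 3: subjects affected (assumptions).** Dropout is spread evenly over Days 11–364 (354 days), and the preceding visit was attended.

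Count = 290 × dropout × attendance × days / 354, with 82 days for Week 26 and 34 days (Days 43–76) for Week 12.

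**Step 4: change in rate, half of these subjects responding**

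- All 290 as denominator: count / 2 / 290.
- Still in trial as denominator: (R·p + count/2) / (R + count) − p, where p is the rate among those remaining and R = 290 − 290 × dropout × 172/354 at Day 182.

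| Dropout / attendance | Week 26 count | Week 12 count | Week 26, of 290 | Week 12, of 290 | R | Week 26, still in trial, p = 40% / 50% / 60% |
|---|---|---|---|---|---|---|
| 10% / 50% | 3.4 | 1.4 | +0.6 | +0.2 | 275.9 | +0.1 / 0 / −0.1 |
| 20% / 50% | 6.7 | 2.8 | +1.2 | +0.5 | 261.8 | +0.2 / 0 / −0.2 |
| 20% / 100% | 13.4 | 5.6 | +2.3 | +1.0 | 261.8 | +0.5 / 0 / −0.5 |
| 30% / 100% | 20.2 | 8.4 | +3.5 | +1.4 | 247.7 | +0.8 / 0 / −0.8 |

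Changes are in percentage points. For scale, the 95% CI half-width for a rate near 50% is 1.96 × √(0.25/290) = 5.8 points.

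**Step 5: a second set of assumptions.** Suppose 2% to 10% of the 290 leave on Days 85–166 after Visit 8, all with an ET score, and 30% to 73.2% of them respond (73.2% is the active-arm rate of the placebo-controlled trial in Protocol 6.3). The rise over 290 is then 0.02 × 0.30 = 0.6 points to 0.10 × 0.732 = 7.3 points.

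**The case against.** The strongest reply is that the rules do not contradict each other. Non-response applies only where a later score is missing, and a re-assigned score is not missing. That is right as a reading, but following the rules in that order is exactly what produces a persistent responder from two scores a day apart. Consistency of wording does not rescue the result.

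Several other points have force.

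- Day 84 followed by Day 85 is an extreme case, and a subject whose last scheduled visit was Visit 7 is filed correctly. However, 82 separate ET days give a too-early Week 26 value.
- The size rests on assumptions. Full attendance is unlikely, since some subjects die or are lost and the protocol asks for the visit only where possible. The spread between Steps 4 and 5 confirms that the size is not anchored. This stands.
- The SAP 8.1 default is that "the percentage denominator will be the number of subjects still in the trial at the respective time point". On that basis the effect is small and has no fixed direction. This stands too, although SAP 13.2.1.2 leaves open whether the default applies once absent subjects are counted as non-responders.
- By-visit plots and MMRM estimates to Visit 11 also bear on durability. The combined status is the only analysis labelled as persistence, not the only relevant one.
- Under the fix, one score is observed in the MMRM but not used for responder status, and ordinary visits remain without windows. The first is a deliberate difference between two questions. The second is tolerable because a subject at an ordinary off-schedule visit is still in the trial.

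**Conclusion.** The concern holds. The misclassification follows from the SAP text alone, under either reading of the rule, provided the preceding visit took place and both scores meet the threshold. The same mechanism reaches the nine-month and twelve-month combined statuses through the 90- and 91-day gaps.

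How many subjects it touches cannot be derived from the documents. Under the Step 3 assumptions it is about 3 to 20 at Week 26 and 1 to 8 at Week 12. All resulting rate changes in Step 4 are below the 5.8-point half-width; only the upper end of Step 5 exceeds it.

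The consequence is confined to exploratory secondary efficacy and by-visit summaries. The primary TEAE endpoint and the overall post-baseline safety summaries are unaffected. The change should be made, but the trial's main conclusion does not depend on it.

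**What to change.** 1. For pain response, combined response and PGIC response, use an early-termination value at a scheduled visit only if its day lies within that visit's protocol window and the visit is not already filled. The windows are ±1 day for Visits 3–5; ±2 days for Visit 6, counted from 4 days after Visit 5 if the treatment period was extended (Protocol 9.3.2); ±7 days for Weeks 6 and 12; and ±15 days for Weeks 26, 39 and 52. For Visits 3–5 in an extended treatment period, where the protocol fixes no day, keep the present assignment. Otherwise the visit is missing and the subject is a non-responder. State the Full Analysis Set as the denominator.
2. Keep the present assignment in the main MMRM, and replace the empty entry in SAP 13.2.2 with a sensitivity MMRM that applies the same windows.
3. Footnote the number of re-assigned out-of-window values in the by-visit BPI, laboratory and bone-marker tables.

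The cost is one SAP paragraph, one programming flag, one model run and some footnotes. Responder counts may fall slightly. No observed score leaves the main MMRM or the by-visit tables, so the commitment in Protocol 14.1.7 to use every post-baseline measurement still holds there.
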